6.5.2 Permitted study drug adjustments

For patients who are unable to tolerate the protocol-specified dosing schedule, dose adjustments are permitted in order to keep the patient on study drug. The recommendations described below should be followed as far as clinically feasible.

All immunosuppressive medication, with single dose, unit, frequency, route of administration, indication, start and end dates will be recorded in the Immunosuppressive Therapies CRF. Only approved but no investigational drugs are permitted.

Oral corticosteroids will be given at a dose of 0.03 – 0.5 mg/kg prednisolone or equivalent throughout the whole trial. If possible, it should remain stable during the entire course of the study. However, dose adjustments for medically indicated reasons will be possible.

Everolimus

Because Everolimus is the mainstay of immunosuppression, Everolimus dose should be continued on a stable level according to trough levels. Dose reductions should only be performed if the symptoms do not respond to other measures (e.g. reduction of MPA dose).

Target therapeutic ranges for Everolimus whole blood trough levels should be 5 - 10 ng/mL.

Dose adjustments may be performed if Everolimus whole blood trough levels outside the target range are measured. Dose adjustments of Everolimus should be monitored 7 days later by a measurement of the Everolimus blood trough level.

In both renal and heart transplantation, Everolimus trough concentrations \leq 3 ng/mL were associated with a significantly lower protection from acute rejection compared with trough levels $>$ 3 ng/mL. Although hyperlipidemias were common over the full exposure range, they responded to corticosteroid dose reduction, dietary management, and lipid-lowering therapies, and were, therefore, not dose-limiting. The incidence of leukocytopenia did not show any exposure-response relationship to Everolimus trough concentrations. The incidence of notable thrombocytopenia ($<$ 100 \times 10⁹/L) increased with Everolimus exposure; however, the incidence of clinically meaningful platelet reductions ($<$ 75 \times 10⁹/L) was generally low.

If Everolimus medication is interrupted for safety related considerations for more than 2 weeks during the Run in phase (Month 3 to Month 6 post Tx) or 4 consecutive weeks within the 12 months study treatment (or cumulative for more than 8 weeks), discontinuation of the medication should be considered and the patient should be withdrawn from study treatment. Appropriate information needs to be recorded on the Dosage Administration CRF.

Cyclosporin A

Target therapeutic range for Cyclosporin A whole blood levels should be the following.

Timepoint	C0-h levels [ng/mL]
Month 3 – 6	100 – 200
Month $>$ 6	50 – 150

Dose adjustments may be performed if Cyclosporin A whole blood levels outside the target range are measured. In case of severe CsA toxicity, dose reductions below the target levels may be performed on the investigator's discretion.

In the CNI-free group the Cyclosporin A will be reduced to a dose resulting in a C0 level of \leq 75 ng/mL starting at Month 6 post Tx and finally (after 8 weeks of reduced dosage) removed completely. At the latest at Month 9, Cyclosporin A should be withdrawn completely from the immunosuppressive regimen in the CNI-free group.

If Cyclosporin A medication is interrupted for safety related considerations for more than 4 consecutive weeks or more than 8 cumulative weeks after randomization, discontinuation of the medication should be considered and the patient should be

withdrawn from study treatment. Appropriate information needs to be recorded on the Dosage Administration CRF.

Tacrolimus

Target therapeutic range for Tacrolimus whole blood levels should be the following.

Timepoint	C0-h levels [ng/mL]
Month 3 – 6	5 – 10
Month > 6	3 – 8

Tacrolimus dosing will be modified by investigators as needed and recorded on the Tacrolimus Dosage Administration CRF at each visit. In the event of Tacrolimus intolerance (e.g. nephrotoxicity, neurotoxicity) dose reduction of Tacrolimus may be necessary. If it occurs that the Tacrolimus trough level is below the required target level, then the investigator will be asked to confirm the intended Tacrolimus trough level, to record the start date and reason for dose reduction on the Tacrolimus Dosage Administration CRF.

In the CNI-free group the Tacrolimus will be reduced to a dose resulting in a C0 level of ≤ 5 ng/mL starting at Month 6 post Tx and finally (after 8 weeks of reduced dosage) removed completely. At the latest at Month 9, Cyclosporin A or Tacrolimus should be withdrawn completely from the immunosuppressive regimen in the CNI-free group.

If Tacrolimus medication is interrupted for safety related considerations for more than 4 consecutive weeks or more than 8 cumulative weeks after randomization, discontinuation of the medication should be considered and the patient should be withdrawn from study treatment. Appropriate information needs to be recorded on the Dosage Administration CRF.

The co-administration of drugs known to interfere with Tacrolimus metabolism should be avoided if possible. If these drugs are required, the investigator must monitor Tacrolimus and/or Everolimus trough levels (Appendices 3 and 4).

Mycophenolic Acid (MPA)

In patients randomized to the CNI-free group, treatment with MPA will be introduced starting the day after Baseline (Month 6 post Tx) assessment (see [section 6.5.1](#)). Either Mycophenolate Mofetil (MMF) or Enteric-Coated Mycophenolate Sodium (EC-MPS) may be applied.

In case of leukopenia (leukocyte count $< 3,000/\text{mm}^3$), neutropenia (neutrophil count $< 1,500/\text{mm}^3$), or anemia, MPA medication doses may be reduced at the discretion of

the investigator or eliminated completely until the event resolves. Furthermore, for any other moderate/severe AE which in the opinion of the investigator warrants a dose reduction or temporary interruption of the medication, this will be allowed. However, the MPA medication should be restarted once the AE has resolved or returned to an acceptable grading (see instructions given in [Appendix 5](#)).

If MPA medication is interrupted for safety related considerations more than 2 weeks during the run in phase (Month 3 to Month 6 post Tx) or for more than 4 consecutive weeks or more than 8 cumulative weeks, discontinuation of the medication should be considered and the patient should be withdrawn from study treatment. Appropriate information needs to be recorded on the Dosage Administration CRF.

The Month 18 assessments will be performed and documented for all patients who are withdrawn prematurely from the treatment at timepoint of discontinuation and again at month 18 after Tx.

In cases of recurrent infections serum antibody concentration should be measured; if hypogammaglobulinemia presents as persistent and clinically significant, patients should be examined accurately and appropriate actions should be taken; dose reduction or change of immunosuppression should be taken into consideration.

Patients with recurrent pulmonary disorders e.g. cough/dyspnea should as soon as possible be examined accurately for signs of bronchiectasis; dose reduction or change of immunosuppression should be taken into consideration.

6.5.3 Rescue medication

Treatment for acute rejection episodes

Patients with presumed acute rejection episodes must undergo endomyocardial biopsy within 48 h (regardless of initiation of anti-rejection treatment) and echocardiogram as needed. If the patient is not stable, the biopsy will be done within 24 hours after the patient has been stabilized. The acute rejection is to be treated according to the following table, or according to local practice. The randomized immunosuppressive regimen should not be changed, unless a second Grade 3A rejection episode with or without hemodynamic compromise occurs or a second rejection episode associated with hemodynamic compromise occurs. If either situation occurs and the investigator chooses to change the randomized immunosuppressive regimen, the patient will be removed from study treatment.

Table 6-2 Acute cellular rejection – diagnosis and treatment

ISHLT biopsy grade 1990 (2004)	Hemodynamic compromise*	
	Absent	Present
Grade 1A, 1B Mild (1R, mild)	No treatment	1-2 mg/kg oral corticosteroids for 3 - 5 days followed by 5 to 10 day taper or immediate return to baseline oral corticosteroids And/or

		High dose IV corticosteroids with or without anti-lymphocyte antibody therapy
Grade 2 Focal Moderate (1R, mild)	No treatment	High dose corticosteroids for 3 days followed by taper or by immediate return to baseline oral corticosteroids And/or High dose IV corticosteroids with or without anti-lymphocyte antibody therapy
Grade 3A, 3B Multifocal or diffuse (2R, moderate or 3R, severe)	1 - 4 mg/kg oral corticosteroids for 3-5 days followed by 5 to 10 day taper or immediate return to baseline oral corticosteroids Or High dose IV corticosteroids for 3 days followed by immediate return to baseline oral corticosteroids	High dose corticosteroids for 3 days with or without 7 - 14 days of anti-lymphocyte antibody therapy followed by a taper or immediate return to baseline oral corticosteroids And/or High dose IV corticosteroids with or without anti-lymphocyte antibody therapy
Grade 4 Diffuse, polymorphous with or without edema, hemorrhage, vasculitis (3R, severe)	High dose IV corticosteroids and anti-lymphocyte antibody therapy	High dose IV corticosteroids with or without anti-lymphocyte antibody therapy

* Hemodynamic compromise is considered to be present if one or more of the following conditions are met:
Ejection fraction \leq 30% or 25% lower than baseline or
Fractional shortening \leq 20% or 25% lower than baseline and/or Inotrope treatment
Baseline is defined as Visit 1

Treatment of CMV

Treatment with gancyclovir, cytomegalovirus hyperimmune globulin, valgancyclovir or valacyclovir is permitted and will be at the investigator's discretion per standard practice of the individual centers. Non-high risk patients will be treated according to local practice. CMV prophylaxis is also recommended following any antibody treatment of acute rejection episodes.

Treatment of *Pneumocystis carinii*

All patients should receive prophylactic treatment for *Pneumocystis carinii* Pneumonia (PcP) with trimethoprim/sulfamethoxazole (e.g. Bactrim[®] or Cotrim[®]) according to local practice. Duration and dosage depend on the discretion of the investigator. Aerosolized pentamidine or dapsone may be administered to patients unable to tolerate oral formulations.

Treatment of Candida

Nystatin for oral thrush (Candida) will be used in a swish and swallow regimen. Routine use of systemic antifungal agents (i.e., ketoconazole, itraconazole, and fluconazole) will not be allowed unless patients are systemically infected. Administration of azoles may increase blood concentrations of Cyclosporin A, Tacrolimus and Everolimus; therefore their use should be minimized. Particular attention to side effects is required. If such agents are to be used, additional drug monitoring Cyclosporin A, Tacrolimus and Everolimus are recommended at start and end of treatment.

Treatment of hyperlipidemia

Lipid lowering medications (e.g. fluvastatin, Lescol[®]) are to be administered to all patients even if the patient does not have an elevated LDL-cholesterol or triglyceride levels at baseline. Initiation of treatment should follow the National Cholesterol Educating Program (NCEP) guidelines (Appendix 6).

The daily starting dose should be the equivalent of 20 mg pravastatin, 5 mg simvastatin, 10 mg atorvastatin, or 20 mg fluvastatin, and may be increased to target and maintain a LDL level of < 130 mg/dL. In case of simvastatin, dose should not exceed 10 mg/day to account for the increased risk of myopathy/rhabdomyolysis, when combined with Cyclosporin A.

When HMG-CoA reductase inhibitors are used concomitantly with gemfibrozil (and probably other fibrates), Cyclosporin A or erythromycin, myopathy and rhabdomyolysis have been reported. **Therefore, the use of lovastatin will be prohibited in this study.**

Lipid lowering medications should be optimized prior to reduction of study medication. If the elevation of cholesterol and/or triglyceride levels persists, the dosing of study medication will be adjusted following the recommendations in Appendix 5.

6.5.4 Other concomitant treatment

The investigator should instruct the patient to notify the study site about any new medications he/she takes after the start of the study drug. All medications (other than study drug) and significant non-drug therapies (including physical therapy and blood transfusions) administered after the patient starts treatment with study drug must be listed on the Prior-/Concomitant medications/Significant non-drug therapies CRF. If required for an AE, such concomitant medication should be cross-referenced on the AE CRF under “action taken”, appropriately coded for “concomitant medication taken”.

Inducers of CYP3A4 (e.g. rifampin, carbamazepine, phenytoin, and barbiturates) have been shown or have the potential to decrease exposure to Everolimus. If these drugs are necessary, Everolimus doses may have to be increased. Potent inhibitors of CYP3A4 such as ketoconazole, itraconazole and fluconazole should be avoided

while the patient is on study medication. Everolimus has the potential to increase the exposure to terfenadine, astemizole and cisapride; hence these drugs should be avoided. In vitro data suggested that everolimus may have the potential to interact with quinidine, fluoxetine and paroxetine, and alternative medications should be considered. Since the potential for drug interaction with digoxin has not been evaluated, patients on digoxin should have periodic measurement of digoxin levels.

The concomitant administration of nephrotoxic drugs (e.g. aminoglycosides, NSAIDs) and drugs known to interfere with Cyclosporin A and Tacrolimus pharmacokinetics (i.e., ketoconazole, erythromycin, phenytoin, barbiturates, carbamazepine, diltiazem, verapamil, rifampin) should be associated with a careful monitoring of renal function and Cyclosporin A / Tacrolimus blood trough levels. In addition, drugs known to interfere with Everolimus or MPA should be avoided (see [Appendix 5](#) for possible drug interactions).

6.5.5 Study drug discontinuation

In case of platelet count < 50,000/mm³, leukocyte count < 3,000/mm³ or neutrophil count < 1,500/mm³, at the discretion of the investigator, MPA medication dose may be reduced by half, or eliminated completely until the event resolves. In case of dose reduction, MPA should be reduced according to the guidelines given in [Appendix 5](#). Everolimus should be continued on a stable dose level and reduced only if the symptoms do not respond to the reduction of the MPA dosage.

In case of elevated cholesterol and/or triglyceride levels, lipid lowering medications should be maximized. If the elevation persists, the dosing of Everolimus should be adjusted following the recommendations given in [Appendix 5](#).

Dose reduction may be performed for those patients with other moderate/severe AEs according to the investigator's judgment. Also in these cases, the medication doses can be reduced by half or interrupted completely until event resolves.

If the MPA or Everolimus medication is interrupted for more than 2 weeks during the run in phase (Month 3 to Month 6 post Tx) or for more than 4 consecutive weeks or more than 8 cumulative weeks within the 12 months study treatment, discontinuation of the respective medication should be considered and the patient withdrawn from study treatment.

Patients who discontinue study drug before completing the maintenance period at Month 18 post Tx should be scheduled for a visit as soon as possible, at which time all of the assessments listed for the final visit (Month 18) will be performed. Month 18 assessments should be repeated at the initially planned timepoint, 18 months post transplantation.

At a minimum, all patients who discontinue study drug, including those who refuse to return for a final visit, will be contacted for safety evaluations during the 30 days following the last dose of study drug.

Patients who discontinue study drug should be considered withdrawn from the study only after the final visit assessments (month 18 post Tx) are performed or when it is clear that the patient will not return for these assessments.

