Appendix 5: Dose Reduction of Everolimus and MPA

Dose reduction or temporary interruption may be performed for MPA or Everolimus. However, Everolimus should be continued on a stable dose level, if possible, and reduced or interrupted only if the symptoms do not respond to the reduction of the MPA dosage.

Implementation of dose reduction will be based on thrombocytopenia, leukopenia, neutropenia, hypercholesterolemia, hypertriglyceridemia, or other adverse events which are suspected to be related to study medication, and in the opinion of the investigator, are clinically warranted. The following guidelines should be used for both dose reduction and restarting or increasing the dose of study medication back to original levels.

In cases of recurrent infections serum antibody concentration should be measured; if hypogammaglobulinemia presents as persistent and clinically significant, patients should be examined accurately and appropriate actions should be taken; dose reduction or change of immunosuppression should be taken into consideration.

Patients with recurrent pulmonary disorders e.g. cough/dyspnea should as soon as possible be examined accurately for signs of bronchiectasis; dose reduction or change of immunosuppression should be taken into consideration.

Dose Reduction Guidelines

Platelets

- platelet count < 100,000/mm³ dose **may** be reduced at the discretion of the investigator
- platelet count < 75,000/mm³ a second dose reduction should be **considered**
- platelet count < 50,000/mm³ **MANDATORY** interruption of medication

WBC

- WBC < 2,500/mm³ dose may be reduced at the discretion of the investigator
A second dose reduction may be implemented if the WBC continues to fall

Dose Reduction	EC-MPS	MMF
Maintenance dose	3 tablets 360 mg b.i.d.	3 capsules 500 mg b.i.d.
Initial dose reduction	2 tablets 360 mg	2 capsules 500 mg b.i.d.
Second dose reduction	1 tablet 360 mg + 1 tablet 180 mg b.i.d..	1 capsules 500 mg + 1 capsule 250 mg b.i.d.

Increase or restart of study medication after a drop in platelets / WBC

Increase dose of study medication following a single dose reduction

After a single dose reduction, full dose of study medications **must** restart if:

- platelet count > 100,000/mm³ (at least 3 days)
- WBC > 3,500/mm³ (at least 3 days)

Increase dose of study medication following a double dose reduction

After a double dose reduction the mid dose of study medications **may** be restarted if:

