- platelet count > 75,000/mm³ (at least 3 days)
- WBC > 3,500/mm³ (stable) (at least 3 days)

the full dose of study medications **must** be restarted if

- platelet count > 100,000/mm³ (at least 7 days)
- WBC > 3,500/mm³ (stable) (at least 7 days)

Restart of dose of study medication following an interruption

After an interruption of study medications (due to a decrease in platelets/WBC) study medication **may** be restarted at the lowest dose if:

- platelet count > 50,000/mm³ (at least 3 days)
- WBC > 3,500/mm³ (stable) (at least 3 days)

the mid dose of study medications **may** be restarted if:

- platelet count > 75,000/mm³ (at least 3 days)
- WBC > 3,500/mm³ (stable) (at least 3 days)

the full dose of study medications **must** be restarted if

- platelet count > 100,000/mm³ (at least 7 days)
- WBC > 3,500/mm³ (stable) (at least 7 days)

Absolute neutrophil count cutoff levels

A decrease in absolute neutrophil counts (ANC) to less than 1,000/mm³ should be avoided during the study. The investigator should use his/her discretion to reduce the dose of non-study medication known to be associated with neutropenia or leukopenia (e.g. ganciclovir, trimethoprim-sulfamethoxazole) before considering initiating a reduction in the dose of study medication.

Recommendations for adjusting the dose of study medication in case of a decrease in absolute neutrophil counts are as follows:

ANC < 1,500/mm³:

Consider dose reduction
(per investigator discretion)

ANC < 1,000/mm³:

Mandatory interruption of study medication

Restart of study medication after a drop in ANC that required interruption of study medication

ANC > 1,500/mm³ for 7 days:

Restart full dose of study medication

Lipid cutoff levels

Evaluations of plasma cholesterol and/or triglyceride levels can result from a number of drugs commonly used in renal transplantation, including study medication, steroids, Cyclosporin A, and other drugs.

If plasma cholesterol and/or triglyceride levels are found to be elevated, the dosing of all concomitant medication potentially affecting cholesterol and/or triglyceride levels should be re-considered and optimized as appropriate, in addition to providing dietary advice.

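### Section 6.5.5 allows half-dose MPA at platelets below 50,000/mm³, where Appendix 5 requires interruption, and its neutrophil rule does not carve out the appendix's mandatory stop below 1,000/mm³

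*Protocol*

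**What the plan says.** Protocol Section 6.5.5 opens with one list of triggers: "In case of platelet count < 50,000/mm³, leukocyte count < 3,000/mm³ or neutrophil count < 1,500/mm³". For all three the response is the same: "at the discretion of the investigator, MPA medication dose may be reduced by half, or eliminated completely until the event resolves". The next sentence points to Appendix 5: "In case of dose reduction, MPA should be reduced according to the guidelines given in" that appendix.

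The MPA paragraph of Section 6.5.2 covers leukocytes below 3,000/mm³, neutrophils below 1,500/mm³ "or anemia, MPA medication doses may be reduced at the discretion of" the investigator, with complete elimination as the alternative. It has no platelet trigger and no lower neutrophil tier. Its reference to Appendix 5 is attached to restarting: "the MPA medication should be restarted once the AE has resolved or returned to an acceptable grading".

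Appendix 5 is stricter at the bottom of each scale. For platelets it allows a first reduction below 100,000/mm³, asks for a second to be considered below 75,000/mm³, and then states: "platelet count < 50,000/mm³ MANDATORY interruption of medication". On neutrophils it says "A decrease in absolute neutrophil counts (ANC) to less than 1,000/mm³ should be avoided during the study". It suggests considering a reduction below 1,500/mm³ and, below 1,000/mm³, orders "Mandatory interruption of study medication".

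The opening paragraph of Appendix 5 covers both MPA and Everolimus. It asks that Everolimus be held stable where possible and changed only if lowering MPA has not worked.

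**The concern.** The body text expressly permits something that the appendix forbids, at an identical platelet count. These are bone-marrow safety stops in patients on combined immunosuppression, and the investigator needs a single answer.

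The difference also carries into other parts of the plan. After randomization, an interruption of more than 4 consecutive or 8 cumulative weeks leads to considering discontinuation and withdrawal from study treatment (Sections 6.5.2 and 6.5.5). A stop starts that clock and a half dose does not. SAP Section 2.4.1 tabulates dose reductions made for safety under the protocol's guidelines. A patient kept on half dose at 45,000/mm³ follows one guideline and departs from the other.

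**Working it through.** No statistical figure is involved. The check compares the rules and works out the doses they imply.

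**1. The rules side by side**

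| Count (per mm³) | Sections 6.5.5 / 6.5.2 | Appendix 5 | Result |
|---|---|---|---|
| Platelets < 50,000 | 6.5.5: halve or stop MPA, investigator's choice; 6.5.2: no platelet trigger | Interruption mandatory | Direct conflict with 6.5.5 |
| Neutrophils 1,000–1,499 | Reduce or stop, investigator's choice | Consider reduction | Compatible |
| Neutrophils < 1,000 | Same discretion; no separate tier | Interruption mandatory | Stricter tier missing from the body |

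**2. Is a half dose an interruption?** Not in Appendix 5's own dose table, where it is a reduction step:
- EC-MPS: maintenance 3 × 360 × 2 = 2,160 mg/day; second reduction (360 + 180) × 2 = 1,080 mg/day; 1,080 / 2,160 = 50%.
- MMF: maintenance 3 × 500 × 2 = 3,000 mg/day; second reduction (500 + 250) × 2 = 1,500 mg/day; 1,500 / 3,000 = 50%.

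The lowest step equals half only at those maintenance doses. At the bottom of the permitted range it is 1,080 / 1,440 = 75% for EC-MPS and 1,500 / 1,500 = 100% for MMF.

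**3. Dose at stake at platelets < 50,000/mm³.** The permitted daily ranges are in Section 6.2.
- EC-MPS: 1,440 / 2 = 720 to 2,880 / 2 = 1,440 mg/day.
- MMF: 1,500 / 2 = 750 to 3,000 / 2 = 1,500 mg/day.
- Appendix 5: 0 mg/day, if MPA is the drug stopped.

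The difference lasts while the count is below the limit. It then continues for at least 3 days above 50,000/mm³ (with WBC above 3,500/mm³), after which the lowest dose may be resumed. After a neutrophil stop, Appendix 5 restarts the full dose once the count has been above 1,500/mm³ for 7 days. Its closing note gives discretion over the dose on restarting, not over whether to stop.

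**4. Do the cross-references settle it?** The one in 6.5.5 takes effect once the investigator has chosen to reduce, so the choice of half dose remains. The one in 6.5.2 concerns restarting. Both lead a reader to the appendix, but neither says that its mandatory stops override the body.

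**5. Which drug does the stop reach?** The CNI group has no MPA after randomization (Table 6-1), and some run-in patients take a CNI with Everolimus and no MPA (Section 6.2). For them an MPA-only stop would act on nothing. Section 6.5.2 reports that notable thrombocytopenia rose with Everolimus exposure, although it describes clinically meaningful platelet falls as generally infrequent.

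**The case against.** The best defence is that the texts can be read together. Stopping MPA complies with both. An investigator who picks the half dose is referred to Appendix 5, where the platelet stop stands among the reduction rules. The neutrophil tier is ordinary detail held in a cited appendix and is consistent with the body's wider discretion.

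Most of this stands for neutrophils: the rule can be found, so the gap is an omission. It does not rescue the platelet rule. Compatibility through the stricter option does not remove an express permission for the laxer one.

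A reader might also infer that Appendix 5 leaves the drug to be stopped unidentified for everyone, because the stop lines speak only of medication or study medication and Section 10.4.1 defines study medication as Everolimus. That goes too far. The appendix's opening paragraph puts MPA first, the dose table beside the platelet and WBC rules lists only EC-MPS and MMF, and SAP Section 2.1.1 counts MPA as study drug. For patients on MPA, the intended drug can be worked out. The real uncertainty concerns patients who are not taking it.

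**Conclusion.** Section 6.5.5 is wrong as written on platelets below 50,000/mm³: it permits 720 to 1,440 mg/day of EC-MPS or 750 to 1,500 mg/day of MMF where Appendix 5 requires interruption. The zero-dose comparison assumes that the appendix means MPA in patients who take it. On neutrophils below 1,000/mm³ the body lacks the appendix's stricter tier, which is a lesser fault.

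Two further inferences are not supported. One is that the matching limits in Appendix 2 prove the stricter rule was intended. Those are reporting flags, and they do not track dosing rules generally: triglycerides are notable at 750 mg/dL but prompt interruption only above 1,000 mg/dL. The other is that trial results are affected. The documents give no frequency for such counts, and nothing here touches the sample size, the type I error or the primary analysis.

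**What to change.** **Section 6.5.5**, replace the first sentence with: *Platelets < 50,000/mm³ or neutrophils < 1,000/mm³: in patients on MPA, MPA must be interrupted; restart per Appendix 5. Leukocytes < 3,000/mm³ or neutrophils 1,000–1,499/mm³: MPA may be reduced or interrupted at the investigator's discretion.*

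**Section 6.5.2 (MPA)**, add the same mandatory interruption for neutrophils < 1,000/mm³.

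**Appendix 5**, keep both stops mandatory and name the drug by situation: *In patients on MPA, interrupt MPA first, and Everolimus only if the count does not respond. In patients not on MPA (CNI group after randomization; run-in patients on CNI plus Everolimus), the mandatory interruption applies to Everolimus.* Simply writing MPA in place of the general term would leave these last patients with no stop at all.

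The cost is a text amendment in three places, with no added visits, data or patients. The Everolimus line needs medical sign-off because it makes explicit what the appendix leaves open. The leukocyte triggers (3,000/mm³ in the body, 2,500/mm³ in the appendix) could be aligned at the same time, but both are discretionary and do not conflict in the same way.

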NB: If a patient is restarting the dose of study medication, the investigator may use his/her discretion with regard to the adjusted dose of study medication, i.e., they are not required to increase doses back to full dose regardless of the platelet or WBC levels, the ANC levels, and/or the cholesterol or triglyceride levels.

Handling of Gastrointestinal Problems

In case of gastrointestinal problems that are caused by the treatment with MPA or Everolimus the first step should be to divide the total daily dose in 3 to 4 single dosages. In case of persisting gastrointestinal complaints, the MPA dosage should be reduced in steps of 360 mg/day until the event resolves.

In the event of gastrointestinal problems that are caused by any other reason (e.g. infections) the medication dosage of MPA and Everolimus should be maintained. Other appropriate actions should be taken based on the investigators' experience and discretion.

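### Section 6.5.5 lets MPA be halved at platelets below 50,000/mm³, where Appendix 5 makes interruption mandatory; by inference, 6.5.5 and 6.5.2 have the same gap at neutrophils below 1,000/mm³

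*Protocol*

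**What the plan says.** Protocol section 6.5.5 opens with three blood-count triggers: "In case of platelet count < 50,000/mm³, leukocyte count < 3,000/mm³ or neutrophil count < 1,500/mm³". For all three it offers the same choice: "at the discretion of the investigator, MPA medication dose may be reduced by half, or eliminated completely until the event resolves". It then adds a pointer to Appendix 5: "In case of dose reduction, MPA should be reduced according to the guidelines given in" that appendix.

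Section 6.5.2, under Mycophenolic Acid, has no platelet trigger. For leukocytes below 3,000/mm³, neutrophils below 1,500/mm³ or anemia, it says "MPA medication doses may be reduced at the discretion of" the investigator, or that MPA may be stopped until recovery. It mentions Appendix 5 only for restarting.

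Appendix 5, whose title names both everolimus and MPA, begins: "Dose reduction or temporary interruption may be performed for MPA or Everolimus". Its platelet list allows a reduction below 100,000/mm³, asks that a second one be considered below 75,000/mm³, and then states "platelet count < 50,000/mm³ MANDATORY interruption of medication". Its neutrophil list asks that a reduction be considered below 1,500/mm³. Below 1,000/mm³ it states "Mandatory interruption of study medication". A closing note says "If a patient is restarting the dose of study medication, the investigator may use his/her discretion with regard to the adjusted dose".

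**The concern.** A mandatory hematologic stop should read the same wherever a site looks it up, and 6.5.5 is the section on study drug discontinuation. A site working from it may keep a patient with platelets below 50,000/mm³ on half-dose MPA, although Appendix 5 requires a stop. A site working from 6.5.5 or 6.5.2 may do likewise with neutrophils below 1,000/mm³.

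The choice also has consequences later in the trial. Under 6.5.2 and 6.5.5, interruption beyond 4 consecutive or 8 cumulative weeks means that discontinuation should be considered and the patient withdrawn from study treatment. A halved dose does not start that clock. Two sites facing the same count could therefore reach different withdrawal decisions, each with protocol text behind it. Protocol 10.4.2 and SAP 2.4.1 tabulate MPA dose adjustments made for safety under the protocol's guidelines, and on this point those guidelines disagree.

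**Working it through.** **Step 1. The MPA rules side by side.**

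| Count (per mm³) | 6.5.5 | 6.5.2 | Appendix 5 |
|---|---|---|---|
| Platelets 50,000 to below 75,000 | no rule | no rule | consider a second reduction |
| Platelets below 50,000 | halve or stop, by choice | no rule | **stop, mandatory** |
| Neutrophils 1,000 to below 1,500 | halve or stop, by choice | reduce or stop, by choice | consider reduction |
| Neutrophils below 1,000 | halve or stop, by choice (inside the below-1,500 range) | reduce or stop, by choice (same) | **stop, mandatory** |
| Leukocytes | below 3,000: halve or stop, by choice | below 3,000: reduce or stop, by choice | below 2,500: may reduce |

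Stopping MPA satisfies every cell. In the two rows marked bold, reducing it complies with the body text and breaches Appendix 5. When the 6.5.5 platelet trigger is first reached, Appendix 5 has already passed through two levels of reduction. The leukocyte cut-offs differ, but each rule is permissive, so neither forbids what the other allows.

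**Step 2. Does Appendix 5 cover MPA?** Its title and first sentence name MPA, and its dose table lists only EC-MPS and MMF. It also has MPA reduced before everolimus. SAP 2.1.1 counts MPA as study drug. Against this, protocol 10.4.1 calls only everolimus study medication. The platelet line says simply medication, so that definition does not reach it. The neutrophil line does say study medication, which is why that limb is slightly less certain.

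**Step 3. Does any link between the texts settle it?** The pointer in 6.5.5 applies once reduction has been chosen and does not remove that choice. The closing note in Appendix 5 concerns restarting. Neither says which text prevails.

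**Step 4. The Appendix 5 dose table (minor note).** Daily dose = units × strength × 2.

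- MMF: 3 × 500 × 2 = 3,000; 2 × 500 × 2 = 2,000; (500 + 250) × 2 = 1,500 mg/day.
- EC-MPS: 3 × 360 × 2 = 2,160; 2 × 360 × 2 = 1,440 (the cell omits the frequency; read as twice daily); (360 + 180) × 2 = 1,080 mg/day.

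From the listed maintenance doses, the first step is 2,000/3,000 − 1 = −33% (EC-MPS 1,440/2,160 − 1 = −33%). The second is 1,500/3,000 − 1 = −50% (1,080/2,160 − 1 = −50%). So the halving in 6.5.5 matches the second step, not the first.

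Section 6.2 permits MMF 1,500–3,000 and EC-MPS 1,440–2,880 mg/day. For a patient on MMF 1,500 the lowest listed dose is also 1,500, a change of 0, so the table has no lower step. For EC-MPS 1,440 it has one: 1,080, or −25%.

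**The case against.** The best defense is that the texts can be read together. An investigator who decides to reduce is sent to Appendix 5, and the first list under its guidelines heading says to stop below 50,000 platelets. A careful reader would then interrupt. That is a possible reading, but it depends on following a pointer about how to reduce and finding there that reduction is not allowed. Section 6.5.5 meanwhile names halving as an option and gives its size. The defense is weaker still for 6.5.2, which refers to Appendix 5 only for restarting.

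On neutrophils, three points stand in part. Section 6.5.5 never prints 1,000, so the conflict there is an inference from the open-ended trigger. Appendix 5 introduces its neutrophil lines as recommendations, although the line itself says mandatory. Section 10.4.1 gives a narrow meaning to study medication. These lower certainty a little; the scope evidence in step 2 outweighs them.

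A reader might also infer from the dose table that a patient on MMF 1,500 mg/day is to be moved up to 2,000 at the first step. The documents do not support that. The rows are labeled as reductions from a listed maintenance dose. Sections 4 and 6.5.1 leave MPA adjustment to clinical judgment, and 6.5.2 allows reduction or stopping without a fixed step. The table is incomplete; it does not instruct anyone to raise a dose.

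**Conclusion.** The point holds as an internal inconsistency in a safety stop rule, wrong as written. It is firm for platelets below 50,000/mm³. For neutrophils below 1,000/mm³ it is slightly less certain, resting on the unbounded trigger and on reading Appendix 5 as covering MPA. The gap in the dose table is a minor note only.

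The number of patients affected is probably small. Platelets below 50,000/mm³ or neutrophils below 1,500/mm³ exclude a patient at enrollment and at baseline, so the count must fall later. After randomization MPA belongs only to the CNI-free regimen, although it may also be used in the run-in. The documents do not say how many patients reach these counts, so no number is estimated. A reader might infer harm to the GFR comparison; nothing in the documents shows that, and it is not claimed.

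**What to change.** In the first paragraph of 6.5.5, replace the single discretionary rule with:

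> Platelets <50,000/mm³ or neutrophils <1,000/mm³: interrupt MPA (mandatory, see Appendix 5). Leukocytes <3,000/mm³ or neutrophils 1,000 to <1,500/mm³: MPA may be reduced (per Appendix 5) or interrupted at the investigator's discretion.

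Make the same neutrophil split in the MPA part of 6.5.2. Leave the third paragraph of 6.5.5, on other adverse events, as it is: it is not limited to MPA, and editing it could change how everolimus is handled.

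Optionally, add a line to Appendix 5 saying that the table applies to the listed maintenance doses, and that a patient already at or below a listed step goes to a lower available dose or is interrupted. For example, MMF 1,500 would go to 1,000 mg/day as 500 mg twice daily.

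The cost is a wording amendment. Table 7-1 already has hematology at every visit, and the stricter rule is the sponsor's own. The SAP reports that enrollment has closed; if treatment has also ended, the clarification still serves the review of protocol deviations and any reuse of this text.
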